### 2.1 Specific Aims

**Specific Aim 1 (Primary Aim):** To evaluate whether the IE intervention will lead to a significantly greater increase in patient sexual function from pre-treatment to post-treatment and 3- and 6-month follow-ups compared to the LHT condition.

**Specific Aim 2 (Secondary Aim):** To evaluate whether the IE intervention will lead to significantly greater improvements in (a) partner sexual function and (b) patient and partner relationship intimacy and quality and psychological distress from pre-treatment to post-treatment and at 3- and 6-month follow-ups, compared to the LHT condition.

**Specific Aim 3 (Secondary Aim):** To evaluate whether increases from pre- to post-treatment in patient sexual communication and self-efficacy for coping with sexual concerns mediate the beneficial effects of the IE intervention on patient sexual function at 3- and 6-month follow-ups.

**Exploratory Aim 1:** To explore whether age ( $\leq 45$  versus  $> 45$  at diagnosis) and race/ethnicity (White versus non-White) moderate intervention effects on the primary outcome of patient sexual function.

**Exploratory Aim 2:** To identify participation barriers and intervention preferences of breast cancer survivors who choose not to participate in the Intimacy Enhancement study.

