### 2.2 Research Hypotheses

**Hypothesis 1:** The IE intervention will lead to an increase in patient sexual function from pre-treatment to post-treatment and 3- and 6-month follow-ups compared to the LHT condition.

**Hypothesis 2:** The IE intervention will lead to significantly greater improvements in partner sexual function, patient and partner relationship intimacy and quality, and psychological distress from pre-treatment to post-treatment and at 3- and 6-month follow-ups, compared to the LHT condition.

**Hypothesis 3:** Increases from pre- to post-treatment in patient sexual communication and self-efficacy for coping with sexual concerns will mediate the beneficial effects of the IE intervention on patient sexual function at 3- and 6-month follow-ups.

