### **4.2.3 Self Report Measures**

#### **4.2.3.1 Primary Outcome Measure (Primary Aim)**

Patient Sexual Function. Patients will complete the primary outcome measure, i.e., the 19-item Female Sexual Function Index (FSFI), at all four time points (T1-T4). The FSFI is a widely used sexual function measure with established validity in breast cancer. The FSFI is an optimal primary outcome measure because it is comprehensive and multi-dimensional, in that it assesses biological, psychological, and social dimensions of women's sexual experiences including desire, arousal, pain, and satisfaction with sexual relationship, all of which may change due to participation in the IE intervention. Further, in our breast cancer pilot trial, we found a very large effect size for patient sexual function (Cohen's  $d=1.30$ ). The total score will be used as the primary endpoint as it reflects women's overall sexual

function. In addition, we will conduct separate models for each sexual function domain as a supplemental analysis to clarify which domains of sexual function may be driving any effects on overall function. FSFI scores are sensitive to increases in response to participation in behavioral (non-medical) intervention trials in women with cancer up to the proposed 6-month time point.

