### **13.5 Statistical Analyses for Aim 3 (Secondary; Mediators of IE Effects on Patient Sexual Function)**

To evaluate whether changes in either sexual communication and/or in self-efficacy for coping with sexual concerns mediate treatment effects on sexual function for patients in the IE condition at 3- and 6-month follow-up, we will use the causal inference framework for mediation described by VanderWeele and others to evaluate whether change (increase) in the mediator variable from pre-treatment to post-treatment mediates improvement (increase) in patient sexual function. Initial models will look for mediation at 3-month follow-up; if evidence of mediation is found, we will also test mediation models which include 6-month follow-up. Effects will be estimated via structural equation modeling, and covariates (age, race, etc.) will be included to account for possible mediator/outcome confounding. Separate models will be fit for the two proposed mediators.

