### **13.8 Power Calculations**

Power calculations are based on Aim 1 (Primary Aim). On the patient sexual function measure, a change of 5 points would be considered clinically meaningful (scale range: 2-36,  $SD \approx 10$ ). Based on pilot data, we anticipate that the  $SD$  of the change scores will be 8.2. Using our prior IE trials to guide attrition estimates, we estimate an attrition rate of 24% at 6-month follow-up, resulting in data available from 92 analyzable couples at 6-month follow-up. We will therefore have 82% power to detect a difference of 5 points in change scores, assuming a 2-sided test with type-I error ( $\alpha$ ) of 0.05. In our breast cancer pilot study, we found a between-groups difference in change scores on patient sexual function of 10.7 at post-treatment. Based on results of similar trials, we expect some attenuation of effects by 6-month follow-up. This study is powered to detect a clinically meaningful change  $> (.5 * \text{main effect})$  through the final assessment point. In sum, the study is conservatively powered to detect an effect of the IE intervention approximately half the size obtained in the pilot trial. The sample size of 120 couples (240 participants) was selected based on these calculations.

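### Aim 3 asks about mediation at 3 and 6 months, but section 13.5 fits the 6-month model only if mediation, by no stated criterion, is found at 3 months

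*Combined protocol and SAP*

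**What the plan says.** Three places name both time points with no condition attached:

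- Section 2.1, Aim 3, asks whether pre-to-post increases in the two mediators "mediate the beneficial effects of the IE intervention on patient sexual function at 3- and 6-month follow-ups".
- Section 2.2, Hypothesis 3, predicts that these increases "will mediate the beneficial effects of the IE intervention on patient sexual function at 3- and 6-month follow-ups".
- The opening sentence of section 13.5 sets out to evaluate whether changes in the mediators "mediate treatment effects on sexual function for patients in the IE condition at 3- and 6-month follow-up".

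Section 13.5 then imposes an order: "Initial models will look for mediation at 3-month follow-up", and "if evidence of mediation is found, we will also test mediation models which include 6-month follow-up". It also states that "Separate models will be fit for the two proposed mediators".

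Section 4.2.3.1 and Table 2 schedule the patient FSFI at baseline, post-treatment, 3 months and 6 months. Table 2 schedules the two mediators at baseline and post-treatment only. Section 13.8 bases its power calculation on Aim 1 and gives none for mediation.

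**The concern.** The condition decides whether the 6-month mediation model is fitted at all, not merely whether its result may be called significant. A secondary aim and its hypothesis name two time points, and only one of them has a guaranteed analysis.

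The condition is also undefined. Section 13.5 does not say whether evidence means a point estimate, an interval or a test, and it sets no alpha. It does not say whether a positive result for one mediator opens the 6-month model for that mediator only or for both. Whether the 6-month analysis exists would therefore be a judgement made after the 3-month results are seen.

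Two things are at stake. A real 3-month indirect effect that the test misses also removes the 6-month answer. And a 6-month indirect effect that is reported will have passed a filter in the same patients, using the same pre-to-post change in the mediator.

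**Working it through.** **1. Aim against analysis**

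| Place | 3 months | 6 months |
|---|---|---|
| Section 2.1, Aim 3 | yes | yes, no condition |
| Section 2.2, Hypothesis 3 | yes | yes, no condition |
| Section 13.5, opening sentence | yes | yes, no condition |
| Section 13.5, planned models | always fitted | only after a positive 3-month finding |

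No other section supplies a 6-month mediation model when the 3-month result is negative. The data for one will exist: the 6-month FSFI is scheduled regardless, and the mediators are complete by post-treatment.

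**2. The plan's only power figure**

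Section 13.8 gives a 5-point difference, SD of change 8.2, 92 analyzable couples (46 per arm at 1:1), two-sided alpha 0.05 and 82% power.

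- Couples: 120 × (1 − 0.24) = 91.2, against 92 stated.
- Normal approximation: 5 / (8.2 × √(2/46)) = 2.924, and Φ(2.924 − 1.96) = 83.3%.
- Noncentral t, 90 df: 82.5%.

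The stated 82% reproduces, but it concerns Aim 1 and says nothing about the chance of passing the mediation condition.

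**3. How often the condition could fail when 3-month mediation is real**

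The documents give no mediator effect size, no mediator-outcome association, no 3-month sample size and no criterion. The following are therefore assumptions:

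- one mediator, with real mediation at 3 months;
- the condition is met when both paths are significant at two-sided 0.05;
- the two path tests are treated as independent;
- n = 92 (the plan's 6-month number) or 96 (20% loss, 120 × 0.80), with 120 (no loss) as an upper limit.

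Formulas, with d the standardised difference between arms in the mediator and r the partial correlation of mediator and outcome:

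- Treatment to mediator: P_a = Φ(d × √(n/4) − 1.96)
- Mediator to outcome: P_b = Φ(atanh(r) × √(n − 5) − 1.96)
- Chance that the 6-month model is not fitted: 1 − P_a × P_b

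Example, n = 92, d = 0.5, r = 0.3:

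- P_a = Φ(0.5 × 4.796 − 1.96) = Φ(0.438) = 0.669
- P_b = Φ(0.3095 × 9.327 − 1.96) = Φ(0.927) = 0.823
- 1 − 0.669 × 0.823 = 0.449

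| d | r | n = 92 | n = 96 | n = 120 |
|---|---|---|---|---|
| 0.3 | 0.2 | 86% | 85% | 78% |
| 0.5 | 0.3 | 45% | 42% | 29% |
| 0.8 | 0.3 | 20% | 18% | 9% |
| 0.8 | 0.4 | 5% | 4% | 1% |

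The entries are chances that the 6-month model is never fitted. If a positive finding for either mediator opened the model for both, the chances would be lower; if both mediators had to be positive, they would be higher. The text does not settle which applies.

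**4. Conditioning**

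The mediator is the pre-to-post change, so the treatment-to-mediator path is essentially the same quantity in the 3-month and 6-month models. If the 6-month model is fitted only when that path and the 3-month outcome path look favourable, the reported 6-month indirect effects will tend to be too large. This concerns the estimate; error rates are taken up under the objection.

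**The case against.** The strongest defence is that section 13.5 states its order openly and in advance. Testing a later time point only after an earlier one succeeds is a recognised way to limit multiplicity, and a pre-specified order does not by itself inflate type I error. A reader might infer that the condition makes the 6-month test invalid; it does not. But the documents give neither a multiplicity reason nor an alpha rule, and limiting significance claims does not require withholding an estimate and its interval.

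A second defence is that Hypothesis 3, read as requiring mediation at both times, already fails if 3 months fails. That is fair for the hypothesis as a single claim, but it does not answer the question about 6 months that Aim 3 poses.

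A third is that little of the trial is touched. That is correct. The intervention effect on sexual function at 6 months is estimated under Aim 1 (section 13.2) whatever happens here. Only the indirect effect, in a secondary aim, is at risk.

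A reader might also infer that the condition will hide mediation that emerges late, with communication changing first and function following. The documents do not support that as the expected pattern. The mediator is measured by post-treatment and the 3-month outcome comes about three months later, so that sequence is already built into the 3-month model. Section 13.8 expects intervention effects to weaken by 6 months, not to grow.

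**Conclusion.** The mismatch stands on the text alone: the aim and hypothesis name 6 months without condition, and the analysis makes it conditional on a finding with no stated criterion. Followed as written, the plan may never produce the 6-month indirect effect.

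The size of the risk is an illustration, not a forecast. With both paths required to be significant and 92 to 96 couples, it runs from about 5% with strong paths to about 85% with weak ones. It would be tempting to choose mid-sized paths and quote a narrower range as the expected loss, but the documents offer nothing from which to choose them, and the result also depends on the unstated criterion and the unstated 3-month sample size.

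This is a cheap improvement to a secondary aim. It does not touch the primary analysis or the sample size.

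**What to change.** In section 13.5, state that the 3-month and 6-month mediation models will be fitted for both mediators in all cases, and that both indirect effects will be reported with confidence intervals. If control of testing is wanted, keep the 3-then-6-month order for significance claims only, and define the criterion (the test and its alpha) separately for each mediator.

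Rewording Aim 3 and Hypothesis 3 to make 6 months conditional, with the condition defined, would also remove the contradiction. It would still leave the 6-month indirect effect unestimated after a negative 3-month result, so it is the weaker repair.

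The cost is one more model and estimate per mediator, on data already scheduled for collection. Keeping the order for claims gives up no multiplicity control.

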#### **4.2.3.4 Moderators (Exploratory Aim), Covariates and Other Measures.**

The moderators of patient age and race/ethnicity will be assessed using medical records and pre-treatment self-report survey, respectively. Covariates. Other socio-demographic characteristics (i.e., education, sexual orientation, marital and work status, income, relationship length) will be assessed through self-report. Medical comorbidity for patients and partners will be obtained by a validated self-report comorbidity measure (Self-Administered Comorbidity Questionnaire, SCQ). In order to reduce participant burden and prevent distress, we have modified this measure for patient participants by removing the item asking whether the participant has cancer. We will keep this item for partner participants. Clinical patient characteristics (e.g. menopausal status, comorbidity, types of treatments) will be obtained through medical chart review. Other Measures. We will collect data on frequency of patient sexual activities and use of sexual aids assessed with items from the PROMIS Sexual Function

measure. We also include two items that we developed and assessed in a prior prospective study in colorectal cancer that assess the extent to which sexuality is important to the individual, based on a theoretical model of flexible coping developed by the PI. We are also including the SexFlex Scale, which is a 6-item scale measuring sexual script flexibility when coping with sexual problems. To assess intervention acceptability, at post-treatment (T2), all participants will complete the CSQ-8 and additional questions assessing ease and helpfulness of participation and therapeutic rapport. Based on Borkovec's research, an intervention credibility measure ("Program Evaluation Form") will be completed after session 1 and again at the post-intervention assessment. All participants will complete surveys after session 1, 2, and 3, and again at the post-intervention survey assessing engagement with the material between sessions ("Materials Review Form"). Lastly, we have included a Coronavirus Impact Scale at baseline and six month follow-up to assess the effects the coronavirus pandemic has had on couples' lives, including their relationship and intimacy.

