### **13.0 Statistical Analysis**

#### **13.1 Overview of Statistical Analyses**

Prior to conducting the primary or secondary analyses, descriptive statistics (i.e., frequencies, measures of central tendency) will characterize the sample in terms of important socio-demographic and clinical characteristics (e.g., age, education, race/ethnicity, and menopausal status) and any other relevant covariates. All outcome variables will be assessed for normality and, if necessary, normalizing transformations may be applied or change scores may be used for outcome measures in analyses. We will describe the interrelationships between all outcomes (primary and secondary) by calculating correlations. To determine whether the enrolled sample differs from eligible study refusers, we will compare these groups on key socio-demographic and clinical factors obtained during screening (e.g., age, treatments) and on severity of sexual concerns using two-sample t-tests or Chi-square tests. Any variables with significant imbalance will be entered in our between groups analyses as covariates. Study completers will also be compared to non-completers on these variables. Every effort will be made to minimize couple drop-out, although some degree of attrition is expected. Logistic regression will be used to understand what factors are predictive of drop-out at the participant level. Factors for possible inclusion in this model include intervention arm, age, level of pre-treatment patient sexual function, and interactions involving intervention arm. Reasons for drop-out will be queried, categorized, and compared within each intervention arm. Our main analyses will account for missing data using multiple imputation with chained equations (MICE). This method will provide valid inferences provided that the probability of having missing data (i.e. drop-out) only depends on the observed data (e.g. treatment arm, baseline sexual function). We chose MICE because it can be used with multi-level models, and it has the ability to readily accommodate categorical variables.

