### **13.2 Statistical Analyses for Aim 1 (Primary Aim; Effects of IE Intervention on Patient Sexual Function)**

The primary analysis will examine whether, relative to the LHT condition, the IE condition leads to greater increases in the primary outcome of patient sexual function at all three post-treatment assessments (T2-4; post-treatment; 3-month FU; 6-month FU). We will also examine specific domains of sexual function (satisfaction, desire, arousal, lubrication, orgasm, pain) separately. In a mixed effects regression model, study condition will serve as the independent variable and patient sexual function at each time point will serve as the dependent variable; pre-treatment sexual function will be included in the model as a covariate with time included as a categorical covariate. Intervention by time interaction effects will be included to test the intervention effect at each follow-up time. Subject-specific random intercepts will account for within-subject variability. Intervention effects on patient sexual function at each follow-up are tested using F tests of combined main and interaction effects.

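### The Aim 3 mediation model does not name baseline FSFI or the baseline mediator as covariates, leaving the mediator-to-outcome path open to modest bias and some loss of power

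*Combined protocol and SAP*

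**What the plan says.** Section 13.5 (Aim 3) sets out to "evaluate whether change (increase) in the mediator variable from pre-treatment to post-treatment mediates improvement (increase) in patient sexual function". Effects are estimated by structural equation modelling within a causal mediation framework, and "Separate models will be fit for the two proposed mediators". The 3-month outcome is tested first, and 6-month mediation is tested only if the 3-month models show evidence of it. The adjustment set is given in one clause: "covariates (age, race, etc.) will be included to account for possible mediator/outcome confounding".

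No other section brings the two baselines into this model:

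- Section 13.2 (Aim 1) does name the FSFI baseline: "pre-treatment sexual function will be included in the model as a covariate with time included as a categorical covariate". Section 13.3 (Aim 2a) refers back to the Aim 1 model, but 13.5 does not.
- Section 4.2.3.4 defines covariates as socio-demographic and clinical: "Other socio-demographic characteristics (i.e., education, sexual orientation, marital and work status, income, relationship length) will be assessed through self-report", plus comorbidity and chart-review items.
- Section 13.1 has a general rule, "Any variables with significant imbalance will be entered in our between groups analyses as covariates", but it follows a comparison of enrolled patients with refusers. It does not select mediator-outcome confounders.

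Table 2 shows FSFI, the communication scale and the self-efficacy items all collected at baseline, so the adjustment is feasible.

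**The concern.** Randomisation protects the path from treatment to mediator. It does not protect the path from mediator to outcome, so the mediation estimate is only as good as the control of confounding on that path.

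With a change-score mediator, women who start low tend to rise and women who start high tend to fall, whatever the treatment does. If women with poor communication or low self-efficacy at baseline also tend to have poor FSFI at baseline, which is plausible but not documented, then mediator change and FSFI change share a cause that age and race do not capture. For an FSFI change outcome the resulting error is positive, the direction that favours Hypothesis 3. Because the 3-month result decides whether 6-month mediation is examined, a wrong first answer carries forward.

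**Working it through.** **The plan's own figure.** No power or precision is stated for Aim 3. For Aim 1, Section 13.8 gives 82% power with 92 couples (46 per arm), a 5-point difference, SD of change 8.2 and two-sided alpha 0.05. The standard error is 8.2 × √(2/46) = 1.710, and 5/1.710 = 2.924. The normal approximation gives Φ(2.924 − 1.960) = 83.3%, and the noncentral t gives 82.5%. The stated figure is reproduced.

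**How strongly baseline FSFI predicts follow-up.** With SD 10 at both times (Section 13.8 gives about 10) and SD of change 8.2, 8.2² = 2 × 10² × (1 − ρ). So ρ = 1 − 67.24/200 = 0.664 and ρ² = 0.44. Baseline FSFI explains about 44% of follow-up FSFI variance.

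**Assumptions not in the documents.** Baseline mediator–FSFI correlation r = 0.2 to 0.6; mediator pre-post correlation (stability) s = 0.5 to 0.7; IE effect on the mediator a = 0.5 SD; mediator SD equal at both times within arm. The 92 couples are the plan's 6-month figure; it gives none for 3 months.

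**Bias when the mediator has no effect.** Within arm, the variance of mediator change is 2(1 − s). Its covariance with FSFI change is (1 − s) × r × (1 − ρ). The spurious slope is therefore r(1 − ρ)/2, whatever s is. Multiplying by a = 0.5 and by 10 FSFI points per SD gives 10 × 0.5 × r × 0.336/2 = 0.84r:

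- r = 0.2: +0.17 points
- r = 0.4: +0.34 points
- r = 0.6: +0.50 points

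For an unadjusted FSFI level outcome the slope is −rρ/2, giving −1.66r: −0.33, −0.66 and −1.00 points.

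**Simulation, no true mediation** (4,000 trials of 92 couples per row; mediation declared if both paths have p < 0.05; indirect effect taken from one sample of 1,000,000):

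| r | s | FSFI change, no baselines: indirect effect, declared | Both baselines: declared | FSFI level, no baselines: indirect effect, declared |
|---|---|---|---|---|
| 0.2 | 0.5 | +0.17, 4.3% | 3.6% | −0.33, 6.1% |
| 0.2 | 0.7 | +0.16, 5.3% | 4.3% | −0.34, 7.2% |
| 0.4 | 0.5 | +0.33, 7.4% | 4.0% | −0.66, 16.2% |
| 0.4 | 0.7 | +0.34, 7.7% | 4.9% | −0.66, 13.8% |
| 0.6 | 0.5 | +0.50, 13.5% | 3.8% | −0.99, 31.4% |
| 0.6 | 0.7 | +0.51, 12.0% | 4.7% | −0.99, 25.8% |

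With both baselines the indirect effect is zero to within 0.01 points in every row. At s = 0.6 the ranges are about 5–14% (change, no baselines), 4–5% (both baselines) and about 7–28% (level, no baselines).

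**A real mediator carrying half of the 5-point effect** (a = 0.5, b = 0.5, s = 0.6; FSFI depends on the mediator net of its baseline). The true indirect effect is 0.5 × 0.5 × 10 = 2.5 points. With FSFI change and no baselines, the expected slope is b(1 + s)/2 + r(1 − ρ)/2 = 0.40 + 0.168r, so the indirect effect is 2.0 + 0.84r: 2.17, 2.34 and 2.50 points at r = 0.2, 0.4 and 0.6. Attenuation from omitting the baseline mediator is partly offset by the spurious positive term. Power is about 73–76%, against 81–84% with both baselines.

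**Baseline FSFI alone.** In the same setting this removes the null bias (false mediation 3.6–4.5%) but recovers only 2.0–2.15 of the 2.5 points, with power 75–78%. In a second setting, with a true indirect effect of 1.0 point acting through the post-treatment mediator level, it recovers 0.52–0.65 points. The baseline mediator is needed as well.

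**The case against.** The strongest reply is that the plan's list is open-ended and its stated purpose is exactly this confounding. That stands. A reader might infer that the plan excludes the baselines; it leaves them unspecified. An open list still does not pre-specify the two covariates most directly tied to change scores, and the choice can alter the result.

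A reader might also infer severe distortion: false mediation in up to 28% of trials (31% at the lowest stability tried), or a real mediator hidden or reversed. Those results belong to a model of follow-up FSFI level with no baseline FSFI. The plan states no such model. Section 13.5 speaks of improvement, which most naturally means change, and where the plan does model FSFI level, in 13.2, it says "pre-treatment sexual function will be included in the model as a covariate". On the change outcome a real mediator is attenuated at most, not cancelled.

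Three further points are fair:

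- The size rests on assumed correlations, and at r = 0.2 the excess of false findings is about one percentage point or less.
- A bias of 0.17 to 0.50 points is about 3% to 10% of the 5-point change that Section 13.8 treats as meaningful.
- Carrying over the Aim 1 covariate alone would remove the false mediation. Nothing in 13.5 says it will be carried over, and it would not remove the attenuation.

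**Conclusion.** The point holds as a gap in specification with a clearly better alternative. For the FSFI change outcome that 13.5 most naturally describes, omitting both baselines roughly triples false mediation at the top of the assumed correlation range and barely moves it at the bottom. It also costs about 8 percentage points of power for a sizeable real mediator. These figures assume linear models without treatment-by-mediator interaction, complete data on 92 couples and the correlations listed above. The bias does not shrink with sample size, so more couples retained at 3 months would make a false finding more likely, not less. The consequence is confined to Hypothesis 3. Aim 1, its power and the sample size are unaffected.

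**What to change.** In Section 13.5, state that baseline FSFI and the baseline value of the mediator under test are covariates in both the mediator equation and the outcome equation, alongside age, race and any other named confounders. Replace the open-ended list with a closed one.

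There is no need to require levels instead of changes. Once both baselines are in both equations, subtracting a baseline from the mediator or the outcome only shifts that baseline's own coefficient. The treatment and mediator coefficients, and hence the mediation estimate, are the same either way. Stating which scoring is used would still help the reader.

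The cost is one sentence and two covariates per equation. All values are already collected at baseline, so no visits, items or participants are added.
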